#### **Sample size**

A minimum sample size of 36 women will be projected, for a confidence level of 95% and a power of 80%, considering 49% avoiding episiotomy in the control group in comparison with 98% in the experimental group (Rodríguez et al., 2017), and divided according to a ratio of 2 women in the control group for every woman in the experimental group. This number will increase in case any women dropped out, such that the final number of participants will be 72, of which 24 will be from the experimental group and 48 the control.

#### **Data Collection**

##### Outcomes

The dependent variables will be age (years), blood pressure (mmHg), weight (kg), BMI (kg/m^2), starting level of physical activity, and tobacco use. These variables will be all measured by experienced personnel at the start of the experimental phase, at two weeks, and again at four weeks after the treatment for both groups had been completed.

Variable relating to childbirth will be measured between the eighth and tenth day after birth by telephone interview and review of hospital medical history. The number of weeks of pregnancy at birth will be measured on a discrete

quantitative scale. Labour onset (spontaneous, stimulated, induced), type of delivery (spontaneous, assisted delivery with forceps, Thierry's spatulas or vacuum extraction, caesarean section), the use of intrapartum pharmacological analgesia (none, epidural anaesthesia, sedatives, nitrous oxide), type of episiotomy (not required, median, lateral, medio-lateral) will be measured by nominal scales, while the degree of perineal tear will be evaluated on an ordinal scale (no injury, degree I: injury to perineal skin; degree II: injury to perineal skin and muscle; degree III: injury to perineal skin, muscle and anal sphincter; degree IV: injury to perineal skin, muscle, sphincter and anorectal mucosa). Weight (kg) and height (cm) will be recorded during the routine antenatal appointments at the health centres using stadiometers with weight scale function. The level of physical activity will be measured using the International Physical Activity Questionnaires (IPAQ) (Craig et al. 2003).

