Although in recent years the practice of routine episiotomies has decreased in Spain, the percentage remains above the recommendations of the WHO (WHO 1999, Escuriet et al., 2015) at around 40.2% (León-Larios et al., 2017). Within this average there is a disparity between the public and private systems, whereby, according to Escuriet et al. (2015), there has been an increase in the number of

episiotomies in private hospitals. In a study carried out in the United Kingdom, Smith et al. (2013) found a difference in the frequency of episiotomies between primiparae and multiparae, and also in the different degrees of perineal tearing, with the most frequent being second degree tears in both uniparity and multiparity contexts (Smith et al., 2013, Zimmo et al., 2017).

In addition, the risk of suffering more serious perineal trauma, specifically fourth degree tears affecting the anal sphincter and recta mucosa is three times greater among primiparae than multiparae (León-Larios et al., 2017, López et al., 2014, OMS 1999).

Perineal wounds suffered during birth significantly increase the risk of PFD, with a consequent impact on the female population of physical and emotional discomfort, depression, social isolation, avoidance of healthy physical activity, and reduction in productivity and quality of life, and a resultant increase in the demands on the health service (Smith et al., 2013, Bozkurt et al., 2014, Pierce et al., 2015, Hyakutake et al., 2016).

Primary prevention of PFD is therefore essential, and the following interventions have been shown to be effective: (i) perineal massage during pregnancy (from week 34) (Oblasser et al., 2016), which has been found to diminish the number of episiotomies in primiparae, shorten the first and second stages of labour, and to reduce postpartum pain in multiparae (León-Larios et al., 2017); (ii) weight management and prevention of constipation through the promotion of a suitable diet and by doing physical exercise adapted to pregnancy (Davidson et al., 2000, Kyvernitakis et al., 2015); and (iii) pelvic floor strengthening exercises, which help to reduce discomfort (mainly among primiparae) and reduce the risk of urinary incontinence in the third trimester of the pregnancy and after childbirth (Hyakutake et al., 2016, León-Larios et al., 2017).

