### **Participants**

A convenience sample of pregnant women attending antenatal classes at health centres in two distinct districts, and meeting the following inclusion criteria:

(i) being registered on an antenatal programme (AP); (ii) giving written consent of participation; (iii) the pregnancy being a singleton; (iv) the pregnancy being low risk; (v) there not being any contraindications for physical exercise (vi) being at least 18 years old.

Women who have missed antenatal appointments, had difficulty in speaking or understanding Spanish, had given birth by caesarean section or declined to participate will be excluded from the study.

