### **Interventions**

The study will be carry out in two stages: the first involved finding Pilates trainers to deliver the sessions, while the second collated participant data from both the experimental and control groups. The first phase took place in November 2018, with the collaboration of two trainers in Huelva and one in Seville, all with the same training background. The second phase will be carried out between December 2018 and December 2019 in the corresponding health centres in Huelva and Seville.

In order to eliminate potential bias as a result of the antenatal classes being deliver by health professionals of different categories, only those health centres where classes are deliver by a midwife were selected for the study. The women participat in the corresponding antenatal classes at the respective centres were

then will be invited to participate in the study either to the experimental group (AC + PM) or in the control group (AC only).

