#### **Data analysis**

The quantitative variables will be presented with the mean and standard deviation, while the qualitative data will be given in frequencies and percentages.

In order to measure the goodness of fit of the quantitative data to a normal distribution, a Lilliefors corrected Kolmogorov-Smirnov test will be used. Bivariate analysis will be carried out with Student's t-test for the comparison of two means. In the case of the qualitative data, the Chi-square test will be used, except when Fisher's exact test was required. Likewise, for the analysis of three or more means, a repeated measures ANOVA will be used to evaluate the effects of the

treatment in the two groups, at baseline, three and five weeks. Correlation between the quantitative variables will be verified using the Pearson coefficient correlation ( $r$ ). Finally, in order to allow for the possibility that the data did not meet the criterion of normality or homoscedasticity, non-parametric versions of the tests above will be also carry out.

Binary logistic regression models adjusted for various qualitative and quantitative predictive variables will be calculated in order to determine association of the variables with perineal trauma in childbirth.

The Odds Ratios (ORs) will be determined with a confidence interval of 95%. The goodness of fit tests ( $-2 \log$  likelihood, goodness of fit statistic, Cox and Snell  $R^2$ , Nagelkerke  $R^2$  and Hosmer–Lemeshow) will be calculated to evaluate the overall fit of the model.

In all statistical analyses, alpha will be set to below 5% / the significance level was established at 5% ( $p < 0.05$ ) and a confidence interval of 95% will be computed. All statistical calculations will be made using IBM SPSS Statistics version 25.0.

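### Parity is neither listed for collection nor named for adjustment, so this non-randomised Pilates comparison is open to confounding of unknown direction and size

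*Combined protocol and SAP*

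**What the plan says.** Recruitment is "A convenience sample of pregnant women attending antenatal classes at health centres in two distinct districts" (Participants). Women in those classes "will be invited to participate in the study either to the experimental group (AC + PM) or in the control group (AC only" (Interventions). No randomisation, matching or stratification is described, and neither the six inclusion criteria nor the exclusions mention parity.

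The Introduction treats parity as related to the outcomes. It cites a UK study that "found a difference in the frequency of episiotomies between primiparae and multiparae, and also in the different degrees of perineal tearing", and says the risk of more serious trauma, specifically fourth-degree tears, "is three times greater among primiparae than multiparae".

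Data Collection – Outcomes itemises what will be recorded. The first list begins "The dependent variables will be age (years), blood pressure (mmHg), weight (kg), BMI" and continues with physical activity and tobacco use. The childbirth list covers gestation at birth, labour onset, type of delivery, analgesia, episiotomy and degree of tear, obtained "by telephone interview and review of hospital medical history". Parity is in neither list.

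Data analysis plans Chi-square or Fisher tests for categorical data. It adds: "Binary logistic regression models adjusted for various qualitative and quantitative predictive variables will be calculated". No covariate is named.

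**The concern.** Where women are not randomised, a variable that predicts the outcome and may differ between groups has to be measured and used. Parity is an obvious candidate here, by the protocol's own account. A team that follows the itemised list would not record it, and the regression could not then include it, however loosely its covariates are described.

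If the Pilates group has fewer first-time mothers than the control group, and first-time mothers have more episiotomies, Pilates will look better than it is. If it has more, a real benefit will be diluted or hidden. Nothing in the documents shows which way an imbalance would run. The aim also covers degree of injury, for which no planned difference is given, so a large expected effect on episiotomy does not protect that outcome.

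**Working it through.** **The plan's own figure.** Sample size assumes "considering 49% avoiding episiotomy in the control group in comparison with 98% in the experimental group", 2:1 allocation, 95% confidence and 80% power. With two-sided 5%, the pooled proportion is (0.98 + 2 × 0.49)/3 = 0.6533, and

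n(Pilates) = [1.960 × √(1.5 × 0.6533 × 0.3467) + 0.8416 × √(0.98 × 0.02 + 0.49 × 0.51/2)]² / 0.49² = 8.91.

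The continuity correction gives (8.91/4) × [1 + √(1 + 6/(8.91 × 2 × 0.49))]² = 11.77, so 12 Pilates and 24 control women, 36 in all. The stated minimum reproduces, so the concern does not rest on a sample-size error. After the allowance for dropout the plan has 24 + 48 = 72.

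**Inputs for the parity check.** The group sizes are the plan's. Parity-specific episiotomy risks and parity shares are assumptions, because the documents give neither. They also do not say which parity group has more episiotomies; a higher risk in primiparae is assumed. The threefold figure concerns fourth-degree tears and is not used as an episiotomy ratio in the tables below.

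**Method.** Risk in a group = share primiparous × primiparous risk + (1 − share) × multiparous risk. For example, 0.6 × 60% + 0.4 × 20% = 44%, and 0.4 × 60% + 0.6 × 20% = 36%. The odds ratio is (0.36/0.64)/(0.44/0.56) = 0.72. Rejection rates come from exact enumeration of two binomials at two-sided 5%, using Fisher's test when the smallest expected count is below 5 and the uncorrected Chi-square otherwise. All of these are for the crude comparison, that is, with parity ignored.

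**No Pilates effect:**

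| Risks, primi/multi | Primiparous share, control/Pilates | Episiotomy, control/Pilates | Spurious OR | False positives, 48/24 | False positives, 24/12 |
|---|---|---|---|---|---|
| 60/20 | 50/50 | 40%/40% | 1.00 | 5.2% | 3.7% |
| 60/20 | 60/40 | 44%/36% | 0.72 | 10.1% | 5.8% |
| 60/20 | 40/60 | 36%/44% | 1.40 | 10.6% | 5.6% |
| 60/20 | 70/30 | 48%/32% | 0.51 | 26.0% | 12.6% |
| 60/20 | 30/70 | 32%/48% | 1.96 | 27.1% | 11.8% |
| 50/25 | 60/40 | 40%/35% | 0.81 | 7.0% | 4.3% |
| 50/25 | 40/60 | 35%/40% | 1.24 | 7.4% | 4.2% |

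**A different set of assumptions.** Hold control avoidance at the plan's 49% and the control group at 50% primiparous. Let the Pilates group range from 20% to 80% primiparous. With a primiparous-to-multiparous risk ratio of 1.5, 2 or 3, parity alone shifts avoidance by up to ±6, ±10 or ±15 points. Fisher's test at 24 and 48 women then rejects in up to 6%, 11% or 21% of trials, against 3.9% with balanced parity.

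**A real effect.** Take risks 60/20 and an odds ratio of 0.25 within each parity stratum, so that Pilates risks are 27.3% and 5.9%. At 24 and 48 women:

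| Primiparous share, control/Pilates | Crude OR | Power of crude test |
|---|---|---|
| 50/50 | 0.30 | 55% |
| 40/60 | 0.41 | 33% |
| 60/40 | 0.21 | 76% |

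The yardstick for confounding here is 0.30, not 0.25: the step from 0.25 to 0.30 arises because odds ratios are not collapsible, even with equal shares.

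**The case against.** **Adjustment is already planned and the hospital history is reviewed.** So the fault may be only an unnamed covariate set. This is partly right: adjustment remains possible if someone extracts parity. But the plan does not commit to extracting it, and a covariate set left open until the data are seen is not prespecified.

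**The figures describe an unadjusted test on all 72 women.** This stands as a limit on their reading. They show what happens if parity is ignored, and the inflation is smaller if dropout or the exclusion of caesarean births leaves fewer women, as the 24/12 column shows.

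**At the planned effect, parity hardly matters.** This is correct at full size. Take control risks of 65% and 30% and a Pilates risk of 2%. With 40% of control and 60% of Pilates women primiparous, control risk is 0.4 × 65% + 0.6 × 30% = 44% and crude power is 99.7%; with 30% and 70% it is 99.2%. The concern is about a smaller effect, and about degree of injury.

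**Every risk and share is assumed, and both groups come from the same kind of midwife-led class.** This is true. The case shows exposure to confounding, not that confounding will occur. A similar source population does not make self-selected groups alike in parity.

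**Sparse cells are a separate problem.** They are, and they would exist without parity. They matter here only for choosing the method of adjustment.

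**Conclusion.** The concern holds. Parity is unrestricted, linked to the outcomes by the protocol itself, missing from both lists of variables and not named for adjustment, in a comparison without randomisation. Direction and size cannot be known from the documents.

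Under the assumptions shown, ignoring parity raises the crude false-positive rate at 24 and 48 women from about 5% to between 7% and 27%. It also moves the power for a moderate real effect from 55% to anywhere between 33% and 76%. The largest spurious difference in the main scenarios is 16 points, against 49 planned, so parity imbalance of this order could not alone explain a result as large as the one planned. It could make a modest result uninterpretable. This should be fixed, but it does not by itself invalidate the study.

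**What to change.** 1. In Data Collection – Outcomes, add parity (primiparous or multiparous), taken at enrolment or from the hospital history already reviewed, and report it by group.
2. In Data analysis, state that the main group comparisons for episiotomy and for perineal injury are stratified by parity or adjusted for it. Keep other covariates few: the plan's rates imply only about 48 × 0.51 + 24 × 0.02 = 25 episiotomies.
3. As a secondary point, name a method that tolerates near-empty cells, such as an exact parity-stratified test or Firth penalised logistic regression. At 98% avoidance, the chance of no episiotomy among 24 Pilates women is 0.98^24 = 62%, and ordinary logistic regression then has no finite group odds ratio. Check that the chosen method is available in the named software; if it is not, name another.

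**Cost.** One data field and slightly more analysis work, with no extra women and no change to the quasi-experimental design. In simulation (4,000 trials in each of five no-effect scenarios with unequal parity), the exact stratified test rejected in 2.8–3.6% and the Firth test in 4.0–5.0%; the median parity-adjusted odds ratio was 0.99–1.01. At the planned effect (3,000 trials, 60% primiparous in both groups, control risks 65% and 30%, Pilates risk 2%), both methods were significant in over 99.9%. The exact test is somewhat conservative. The case for recording parity does not depend on these simulations.

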#### Experimental group

The experimental group will receive two one-hour Pilates sessions per week over a period of 4 weeks (Table 1). In addition, the participants will receive their usual antenatal classes at their respective health centres in accordance with the Comprehensive Healthcare Programme for Pregnancy, Childbirth, and Postpartum (CHPPCP) from the Andalusian Regional Government (Aceituno et al. 2014).

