#### Control group

The control group will receive solely the antenatal classes at their corresponding centres as programmed (Table 2).

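### No gestational-age entry window, control starting point or record of gestation at entry, so unadjusted comparisons of weeks at birth and of serial weight, BMI and blood pressure may be confounded by gestational stage

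*Combined protocol and SAP*

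**What the plan says.** **Entry.** The Participants section lists six inclusion criteria, beginning "i) being registered on an antenatal programme (AP); (ii) giving written consent of participation; (iii) the pregnancy being a singleton". The others concern low risk, fitness for exercise and adult age. None names a gestational week. The exclusions, "Women who have missed antenatal appointments, had difficulty in speaking or understanding Spanish, had given birth by caesarean section or declined to participate", apply to both groups alike.

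**Allocation.** Under Interventions, women at midwife-led antenatal classes are invited "either to the experimental group (AC + PM) or in the control group (AC only" arm). The Design section calls the study quasi-experimental.

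**Exposure.** "The experimental group will receive two one-hour Pilates sessions per week over a period of 4 weeks", with detail in Table 1. For controls: "The control group will receive solely the antenatal classes at their corresponding centres as programmed (Table 2"). Neither table is in the text available to us, and the visible text gives no start week for either group.

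**Measurement.** Under Outcomes, age, blood pressure, weight, BMI, starting physical activity and tobacco use are taken "at the start of the experimental phase, at two weeks, and again at four weeks after the treatment for both groups had been completed". Weight and height are recorded at routine antenatal appointments. Gestation appears only as a birth variable: "The number of weeks of pregnancy at birth will be measured on a discrete" quantitative scale.

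**Analysis.** The Data analysis section uses a t-test for two means and a repeated-measures ANOVA for treatment effects, with time points at baseline and weeks 3 and 5. Non-parametric versions are also planned. The only adjusted models are logistic regressions for perineal trauma.

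**The concern.** Weight, BMI and blood pressure depend on how far the pregnancy has advanced. When groups are not randomised and entry week is neither fixed nor recorded, a group difference in these measures cannot be separated from a difference in gestational stage. Control women have no experimental phase, so the visible text does not say when their clock starts.

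Weeks of pregnancy at birth has a related problem. A woman must be undelivered to enter, so later entry in one group raises that group's mean by selection. The same happens, more strongly, if women who give birth during the four-week course are removed from the Pilates group while controls, who have no such course, stay in. The Sample size section allows for drop-outs without defining them, and no analysis set is stated.

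Last, a late entrant may have given birth before her final serial measurement. The plan has no rule for that value, and a conventional repeated-measures ANOVA discards any woman with an incomplete series, which leaves those who stayed pregnant.

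**Working it through.** The plan gives no figure for timing. Its one calculated figure, the minimum of 36 women, reproduces as 12 + 24 (two-sided 5%, 80% power, 2:1, continuity correction) and is unaffected by this point.

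**Step 1: when the last measurement falls.** Let g be the week of entry and d the delay to the last measurement.
- Outcomes, four weeks counted from the start: d = 4.
- Data analysis, last time point: d = 5.
- Outcomes, four weeks counted from the end of a four-week course: d = 4 + 4 = 8.

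The measurement precedes a birth at week B only if g ≤ B − d.

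| Reading | B = 40 | B = 37 |
|---|---|---|
| d = 4 | g ≤ 36 | g ≤ 33 |
| d = 5 | g ≤ 35 | g ≤ 32 |
| d = 8 | g ≤ 32 | g ≤ 29 |

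No entry rule in the visible text secures any of these limits.

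**Step 2: how many women this could touch.** Assumption, not in the documents: gestation at birth is normal with SD 1.3 weeks and mean 39.0 to 40.0. Share still pregnant at g + d = P(birth > g + d) / P(birth > g). Example, g = 34, d = 4, mean 39.0: P(Z > (38 − 39)/1.3) = P(Z > −0.769) = 0.779, and the denominator is 1.000 to three decimals.

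| Entry week | +4 weeks (course end) | +5 weeks | +8 weeks |
|---|---|---|---|
| 32 | 98.9–99.9% | 93.8–98.9% | 22.1–50.0% |
| 34 | 77.9–93.8% | 50.0–77.9% | 1.1–6.2% |
| 36 | 22.3–50.1% | 6.3–22.1% | 0.0–0.1% |

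Of the 24 Pilates women planned, the number giving birth before the course ends would be 24 × (1 − share): 0.0 to 0.3 for entry at week 32, 1.5 to 5.3 at week 34, and 12.0 to 18.6 at week 36.

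**Step 3: possible bias in weeks at birth.** Under the same assumption, the mean among women undelivered at week t is μ + 1.3 × φ(a)/P(Z > a), with a = (t − μ)/1.3.

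- *If mid-course births were dropped from the Pilates group only*, the bias is the mean at t = g + 4 minus the mean at t = g. For g = 34 and μ = 39.0: 1.3 × 0.2968/0.7791 = 0.50 weeks. For μ = 40.0: 1.3 × 0.1222/0.9380 = 0.17 weeks. By the same formula, entry at week 32 gives 0.005 to 0.04 weeks and entry at week 36 gives 1.0 to 1.7 weeks.
- *If nobody is dropped but one group enters at week 36 and the other at week 32*, the difference is 0.005 to 0.04 weeks. Later entry alone matters little until it nears term.

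**The case against.** A reader might infer that the Pilates group is necessarily weighted towards women who stay pregnant. The documents do not support that. Nothing makes course completion a condition of being counted, nothing drops or reclassifies a woman who gives birth mid-course, and the exclusions apply to both groups. The dropping scenario is something the plan leaves open, not something it says.

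It is also fair that both groups come from the same midwife-led classes, that one sentence sets measurement times for both, and that Tables 1 and 2 may carry timing. This could narrow the spread of entry weeks. It would not put gestation at entry into the data or the analysis.

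On serial measures, unequal entry weeks need not produce a treatment-by-time effect. If a measure changes at a constant weekly rate, a gap in entry week shifts every time point equally and the interaction is zero; what remains is a difference in level. A spurious interaction needs a rate that varies with gestation, or births falling between measurements. Because weight is taken at antenatal appointments, a delivered woman's weight and BMI are more likely to be missing than post-birth. Both points stand.

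A reader might also think the problem beyond repair once data are collected. That goes too far: with dates of entry and birth, gestation at entry follows by subtraction from weeks at birth. The plan does not list those dates, however, and back-calculation cannot create a common window or restore missed measurements.

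Finally, the aim, hypothesis and sample size concern perineal injury and episiotomy, and no effect on these is shown.

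**Conclusion.** The point holds as a risk of confounding and selection in secondary comparisons. In a non-randomised study the plan compares serial measures and weeks at birth without fixing, recording or adjusting for gestation at entry, and without a stated time zero for controls. That the ANOVA covers weight, BMI and blood pressure, and the t-test weeks at birth, is our reading of the general wording of the Data analysis section.

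The size depends on entry week, which the visible text does not give. Under the assumed birth distribution, loss of women by course end is negligible for entry at week 32 and large at week 36. The bias in weeks at birth ranges from near zero to about 1.7 weeks, and then only if mid-course births are dropped from one group. The timing limits in Step 1 need no distributional assumption. Separately, the measurement times under Outcomes and Data analysis disagree and must be reconciled whatever the entry week.

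**What to change.** 1. **Outcomes and Data analysis:** reconcile the measurement times into one schedule. The rest depends on this.
2. **Outcomes:** record gestational age at entry for every woman, and start the clock at the same entry visit in both groups.
3. **Participants:** state one gestational-age window for entry, chosen by the sponsor and identical for both groups. If Table 1 or 2 already implies one, make it an explicit criterion.
4. **Data analysis:**
   - Analyse each woman in the group she joined, whether or not she completed the course.
   - Replace the unadjusted comparison of weeks at birth with a regression on group and gestational age at entry.
   - Analyse pre-birth serial values with a mixed model, available in SPSS, adjusted for gestational age at entry. This keeps women with incomplete series; merely deleting post-birth values and running the ANOVA would drop those who give birth early and recreate the selection. Where the rate of change may vary with gestation, include entry gestation by time.

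The cost is revised wording in three sections, one extra variable, and slightly slower recruitment because some attenders will fall outside the window. The mixed model assumes that missing later values are explained by what has been recorded, which is more plausible once gestation at entry is in the model.
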